4.2 Study Design Review

The sponsor has continuously monitored the overall (pooled) event and drop-out rates during the course of the study. Sample size may be increased during the study to maintain the planned target of 113 events. Only pooled blinded data will be used to increase sample size.

5 EFFICACY AND SAFETY ENDPOINTS

This section lists the study's efficacy and safety variables. Section 7 of the study protocol provides details regarding the description, timing, and collection of the variables. See the schedule of events in [Appendix 1](#) of the study protocol.

5.1 Efficacy Endpoints

The efficacy analyses are defined in three stages for statistical inference. Stage 1 refers to the primary efficacy endpoint; Stage 2 to the key secondary endpoints; and Stage 3 to the other secondary endpoints. Section [6.10](#) addresses the planned formal testing to ensure control of type 1 error rate.

5.1.1 Primary Efficacy Endpoint (Stage 1)

The primary efficacy endpoint is the time to first occurrence of clinical worsening (see Section [2.1](#)). The time is defined as follows:

Time-to-clinical-worsening (TtCW, in days) = Date of first EAC-confirmed clinical worsening – Date of randomization + 1.

In addition to the primary composite endpoint, individual components of TtCW (Section [2.1](#)) will be presented and examined in an exploratory manner (see Section [6.12.7](#)).

5.1.2 Key Secondary Endpoints (Stage 2)

The study has the following three key secondary efficacy endpoints:

1. TtCF as defined in Section [2.2](#).
Time-to-clinical-failure (TtCF, in days) = Date of first clinical failure composite endpoint – Date of randomization + 1
2. Exercise capacity at Week 24 as measured by the change from baseline in distance walked on a 6MWT
3. PAH status at Week 24, as defined as the change from baseline in WHO Functional Class

5.1.3 Other Secondary Endpoints (Stage 3)

The study has the following other secondary outcomes:

- Outcomes at 24 weeks – change from baseline in the following:
 - Borg Dyspnea Score
 - NT-pro-BNP levels
- Total mortality (censored at last contact if lost to follow-up or if vital status is missing at study termination)

5.1.4 Exploratory Endpoints

- [REDACTED] [REDACTED]
[REDACTED]
[REDACTED]
[REDACTED]
[REDACTED]

[REDACTED]
[REDACTED]
[REDACTED]
[REDACTED]
[REDACTED]
[REDACTED]
[REDACTED]
[REDACTED] [REDACTED]

5.2 Safety Variables

The following safety variables will be assessed:

- AEs
- Clinical laboratory parameters
- ECG findings
- Vital signs

5.3 Exploratory Endpoints

[REDACTED]
[REDACTED]
[REDACTED]

6 STATISTICAL METHODS

6.1 Datasets for Analyses

This study has the following three analysis populations:

- Randomized Population: All subjects randomized to the study. Tabulations for disposition of subjects will be generated from this population.
- Full Analysis Set (FAS) Population: All randomized subjects who received at least one dose of IMP (esuberaprost or placebo) in the study. Efficacy analyses will be conducted on this population. Subjects whose randomized treatment differs from the actual treatment received will be classified in their randomized treatment group.
- Safety Analysis Population: All randomized subjects who received at least one dose of IMP. Safety analyses will be conducted on this population. Subjects whose randomized treatment differs from the actual treatment received will be classified in the treatment group for actual treatment received. A subject who received some esuberaprost and some placebo will be assigned to the esuberaprost group.

A summary table presenting the number and percentages of subjects for each analysis populations will be presented by treatment group.

After the study database is locked and before treatment codes are unblinded, the sponsor will generate the list of subjects to be excluded from the FAS and Safety Analysis Populations.

The sponsor must approve this list before treatment is unblinded and thus before performing any analyses.

6.2 General Methodology

Treatment groups will be described as “Esuberaprost” and “Placebo” to correspond with esuberaprost with inhaled treprostinil and placebo with inhaled treprostinil, respectively.

Subjects who are not retained will not be replaced during the study; the data analysis will include the subjects who were not assessed in a manner described in the various sections that follow. Subjects completing the study will be defined as those on study, whether or not they have remained on IMP at time of the close of study or those subjects who have experienced a clinical worsening event during the study. Early terminations from the study or IMP for any other reason will be identified.

If an evaluation is repeated, such as to confirm an observed aberrant laboratory value, the analyses will use the later value. Evaluations from Unscheduled Visits are to be included with Scheduled Visits following these rules to the extent possible.

Continuous variables will be summarized with standard descriptive statistics such as mean, standard deviation, median, 25th and 75th percentiles, minimum, and maximum. For categorical data, descriptive analyses will be based on the number of subjects and related percentages.

Tabular presentations will display two columns of results, one for each treatment group, with the labels “Esuberaprost” and “Placebo”. Throughout this analysis plan, the phrase “by treatment group” will refer to these two groups. If useful, some tables will include a third column representing the total population.

All tables will be presented in landscape format. For practical reasons, the point size may be reduced to (but not less than) 7 point for tables that contain too much information to fit into a single page. SAS version 9.3 or higher (2011) will be used. The sponsor’s Biostatistics Department will analyze the efficacy and safety data.

Prior to unblinding, an addendum will be written that will describe the data conventions to be used to implement this SAP.

6.3 Definition of Analysis Time Points

6.3.1 Baseline

The protocol designates two days as ‘baseline’ for the protocol Baseline Visit: Day 1 (the day on which the subject is randomized) and Day 2 (the day the subject is first administered IMP). Analyses designated as a change from baseline will use the results of evaluations collected on the Day 1 Visit as the baseline, except for analyses of the 6MWT and Borg Dyspnea Score data, which will use the average of the Day 1 and Day 2 values. In the case of a single, missing Baseline Visit Day 1 or Day 2 value for 6MWT or Borg Dyspnea Score, the single value will be used as baseline.

For other variables, the baseline value will be defined as the value immediately prior to randomization. For some measures, the baseline will be as defined as the last evaluation closest to, but prior to, the first dose of IMP. If helpful for clarity, analyses will specify the time of baseline.

6.3.2 Change from Baseline

For parameters measured at baseline, the variables of interest are the change from baseline of the original measurements. Unless otherwise specified, all changes from baseline (for all variables where this is applicable) will be calculated as follows:

$$\text{Change from baseline} = \text{Post baseline} - \text{baseline}$$

6.3.3 Study Day

Study day will be calculated relative to randomization (Baseline, Day 1). Specifically:

$$\text{Study day pre-randomization} = (\text{Date of occurrence} - \text{Date of randomization}).$$

$$\text{Study day on or post-randomization} = (\text{Date of occurrence} - \text{Date of randomization}) + 1.$$

6.3.4 Visit Windows

Evaluations will be counted as occurring at the Scheduled Visit designated by the protocol and as recorded on the eCRF irrespective of deviations from protocol-specified visit windows.

Unscheduled Visits will be mapped to Scheduled Visits for the purposes of analyses or summaries according to the following rules:

- Evaluations observed at Unscheduled Visits will be mapped to the Scheduled Visits if, and only if, the evaluations for that Scheduled Visit are missing and within a logical visit window. If more than one Unscheduled Visit is present, then the evaluation closest to the projected Scheduled Visit will be used.

The following rule will apply for mapping Unscheduled Visits to missing data for End of Study Visits:

- Evaluations observed at an Unscheduled Visit will be allotted to an End of Study Visit if, and only if, the End of Study Visit evaluations are missing and the Unscheduled Visit occurred on the same day as the End of Study Visit.

The following rule will apply for mapping End of Study Visits to Scheduled Visits:

- The End of Study Visit will be mapped to the next Scheduled Visit if the subject has completed the study, the End of Study Visit occurs within the window of the next planned Scheduled Visit, and the subject has not changed the dose of IMP. For example, this rule applies to the last site visit before a subject is transferred to an open label extension study while the subject is on IMP but not to subject who has weaned from study drug during early termination.

6.4 Data Handling

6.4.1 Stratification Variable

Subjects are randomized using a centrally administered randomization scheme stratified by use of inhaled treprostinil (current user at the time of the Screening Visit: yes or no) (Section 3.2.4). The clinical site enters the subject's inhaled treprostinil experience into the IRT system. If data entry errors occur and subjects are incorrectly stratified, no changes will be made to the assigned randomization, but subjects will be reclassified into the correct stratum for statistical analyses based on data from the concomitant medications CRF (100% source verified).

6.4.2 Handling of Missing Data

The sponsor acknowledges the implications of missing data on the integrity of study outcomes and, consistent with Fleming's recommendations (2011), implemented the following strategies to minimize the extent of missing data:

1. All subjects were allowed to continue in the study until the close of study, whether on IMP or not. Subjects were not to be summarily discontinued from the study, unless 1) the subject withdrew informed consent; 2) the subject met a primary endpoint and declined continuation in the study; or 3) the subject continued to be non-adherent to study protocol after repeated attempts to correct (at least 6 months). However, the subject has the right to discontinue from the study at any time. All subjects who discontinue the study, unless they withdraw informed consent, will continue to be followed, to the extent possible, for vital status until the sponsor concludes the study.
2. Recent publications (Sitbon et al., 2015; Galiè et al., 2015) have shown that roughly 20% of subjects prematurely terminate from mortality and morbidity studies in PAH. The sponsor has throughout the study engaged with study investigators to encourage subjects' retention in the study, adherence with the protocol, and compliance with IMP.
3. While the study protocol is necessarily complex in order to obtain the scientific data to evaluate the safety and efficacy of the IMP, the sponsor designed the protocol in the manner that was not burdensome to the subjects: 1) Much of the data collected for secondary endpoints is derived from assessments performed for 'standard of care' visits; 2) Study visits are minimal (quarterly) with permissive visit windows (\pm 10 days); 3) Use of optional substudies for exploratory endpoints; and 4) Sponsor-provided Tyvaso to all subjects in the study.

Methods for handling missing data will be described in the sections discussing each outcome.

No imputation is planned for missing safety or exploratory data.

6.5 Disposition of Subjects

The Randomized and FAS analysis populations will be used to describe subject disposition. The number and percentage of randomized subjects who completed and who discontinued (with reason for discontinuation) will be summarized by treatment group. In addition, a summary table will show subject status by clinical site.

A CONSORT diagram (Schulz et al 2010) will display the disposition by treatment group.

6.6 Protocol Deviations

Significant protocol deviations occurring during the study, major or minor, that could impact the completeness, accuracy, and/or reliability of the study data or that may affect a subject's rights, safety, or well-being will be determined by the sponsor (which will be completed prior to database lock) and will be presented for all subjects randomized.

6.7 Demographic and Other Baseline Characteristics

The following summaries will be based on the FAS population.

6.7.1 Demographic and Baseline Characteristics

Descriptive statistics will be presented overall and by treatment group for the following demographic data at randomization:

- age (in years);
- age (<65, \geq 65 years);
- sex (males, females);
- race (white, black or African-American, Asian, other);
- ethnicity (Hispanic or Latino, non-Hispanic or Latino);
- weight (in kg);
- height (in m);
- BMI (in kg/m²);
- smoking status (never, former, current smoked cigarettes/cigars); and
- country of clinical site (US, Israel).

6.7.2 PAH Disease Characteristics

Descriptive statistics presented overall and by treatment group for subjects' PAH history at randomization will include the following:

- PAH etiology [idiopathic or familial, associated with collagen vascular disease, associated with HIV infection, induced by anorexigens/toxins, associated with repaired congenital systemic-to-pulmonary shunts (repaired \geq 1 years)];

- background PAH therapy (Endothelin receptor antagonist [ERA], Phosphodiesterase Type 5 Inhibitor [PDE-5 inhibitor], inhaled treprostinil [experienced or naïve], and riociguat);
- background inhaled treprostinil (experienced or naïve)
- age of PAH diagnosis (date of diagnosis minus date of birth, in years);
- years of PAH (date of Screening Visit minus date of diagnosis);
- 6MWT and Borg Dyspnea Score at Screening;
- baseline average 6MWT;
- baseline average Borg Dyspnea Score; and
- baseline WHO Functional Class.

6.7.3 Medical History

Medical conditions and surgical history identified prior to randomization will be summarized overall and by treatment group. The number and percentage of subjects with any occurrence will be summarized by System Organ Class (SOC; alphabetically) and by preferred term in decreasing order of incidence.

For subjects experiencing the same medical condition multiple times, the summaries will count the condition only once for the corresponding preferred term. Similarly, the summaries will count a subject with multiple medical conditions within the same SOC only once for that SOC. SOCs will be tabulated alphabetically; within each SOC, preferred terms will be presented in decreasing order of incidence.

Medical conditions are coded according to the Medical Dictionary for Regulatory Activities (MedDRA) coding dictionary (the database will document the version current at time of data lock).

6.7.4 Medications

All medications will be coded using the WHO-Drug Global Dictionary (the database will document the version current at time of data lock).

Medications will be summarized overall and by treatment in two separate analyses, one for prior and one for concomitant medications. The number and percentage of subjects with any medication will be summarized by decreasing order of incidence. The number and percentage of subjects who have taken a medication within a primary drug category will be summarized by treatment group under that drug category by the most specific level available.

For these summaries, a subject taking the same medication multiple times will only be counted once for the corresponding most specific level available. Similarly, a subject who took multiple medications within the same drug category will be counted only once for that drug category. Prior medications will be presented in alphabetical order of drug category; within each drug category, drug most specific level available will be presented in decreasing order of incidence.

6.7.4.1 Prior Medications

Any medication or therapy reported before the first dose of IMP will be considered a prior medication.

6.7.4.2 Concomitant Medications

Any medication or therapy initiated after the first dose of IMP during the study will be considered a concomitant medication.

In addition, summary tabulations may be prepared to illustrate the extent and use of: 1) P-glycoprotein and BCRP inhibitors taken with IMP; 2) Concomitant meds that may be of interest from potential drug-drug interactions with IMP; and 3) Concomitant medications that are commonly co-administered for the treatment of PAH.

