5.2 Inclusion Criteria

The following are inclusion criteria to be enrolled in this study:

- 1. Male or female, age 18 to 80 years (inclusive).
- 2. Established diagnosis of pulmonary arterial hypertension that is either idiopathic or familial PAH, collagen vascular disease associated PAH, PAH associated with HIV infection, PAH induced by anorexigens/toxins, or PAH associated with repaired congenital systemic-to-pulmonary shunts (repaired ≥1 years).
- 3. If HIV positive, has a CD4 lymphocyte count ≥200 cells/mm3 within 30 days of Baseline Visit and is receiving current standard of care anti-retroviral or other effective medication.
- 4. At the Screening Visit, WHO functional class III or IV and who have declining or unsatisfactory clinical response to current PAH therapy.
- 5. At the Baseline Visit, WHO functional class III or IV and who have declining or unsatisfactory clinical response to inhaled treprostinil therapy.
- 6. Able to walk unassisted (oxygen use allowed).
- 7. A 6-Minute Walk distance (6MWD) of \geq 100 meters at the Screening Visit.
- Previous (within five years prior to the Baseline Visit) right heart cardiac catheterization (RHC) with findings consistent with PAH, specifically mean Pulmonary Arterial Pressure (PAPm) ≥25 mmHg (at rest), Pulmonary Capillary Wedge Pressure (PCWP) (or left ventricular end diastolic pressure) ≤15 mmHg, and Pulmonary Vascular Resistance (PVR) >3 mmHg/L/min.¹
- 9. Echocardiography excluding any clinically significant left heart disease (e.g. left sided valve disease, wall motion abnormality suggesting of myocardial infarction, left ventricular hypertrophy, etc.).
- 10. Pulmonary function tests conducted within 12 months before or during the Screening period to confirm the following:
 - a. Total lung capacity (TLC) is at least 60% (predicted value); and
 - b. Forced expiratory volume at one second (FEV1) of at least 50% (predicted value).
- 11. Subjects receiving additional FDA approved PAH therapies must be stable on their current dose for at least 30 days prior to the Baseline Visit, apart from modification of anticoagulant or diuretic dosages.
- 12. Must have completed 90 days of uninterrupted inhaled treprostinil treatment and received a stable dose of inhaled treprostinil for at least 30 days prior to Baseline to be eligible for randomization into the study.

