7.2 Medical History

Medical and surgical history will be collected from each subject during the Screening Visit and updated at the Baseline Visit, as applicable. The medical and surgical history will focus on relevant and significant past or present illnesses. The history will cover relevant areas such as head, eyes, ears, nose, and throat, cardiovascular; respiratory; abdomen; gastrointestinal/liver; kidney/urinary, genitalia/reproductive, musculoskeletal; endocrine, history of allergies or idiosyncratic responses to drugs, psychiatric, neurological; dermatologic, and extremities. This information will be used for assessing whether subject meets inclusion/exclusion criteria.

Current prescription and/or nonprescription medications will be assessed and entered in the concomitant medications CRF to enable tracking of any changes to prior medications which occur during the study. Nonprescription medications include vitamins and herbal preparations.

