7.13 Concomitant Medication Assessments

Concomitant therapy includes any prescription and/or nonprescription medications taken in combination with study drug. All concomitant medications will be followed during the study and entered on the appropriate page of the CRF. Nonprescription medications include vitamins and herbal preparations.

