10.6 Concomitant Therapy

Concomitant medications (medications present while on study drug) will be recorded throughout the study. These medications will be coded using the WHO drug dictionary. The number of randomized subjects using prior or concomitant medications will be categorized by the WHO drug category and preferred term, and presented for each treatment group. In any given category [e.g., drug category] a subject will be counted only once.

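### The SAP counts only drugs started after first dose as concomitant, against the protocol's overlap definition, so neither medication table shows what was taken alongside IMP

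*SAP*

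**What the plan says.** SAP 6.7.4 plans "two separate analyses, one for prior and one for concomitant medications". Two short definitions follow. Under 6.7.4.1, "Any medication or therapy reported before the first dose of IMP will be considered a prior medication". Under 6.7.4.2, "Any medication or therapy initiated after the first dose of IMP during the study will be considered a concomitant medication". Nothing in these sections puts a drug that continues past first dose into both tables, and nothing separates stopped from ongoing drugs within the prior table.

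SAP 6.7.4.2 then allows three further tabulations, all optional: (1) P-glycoprotein and BCRP inhibitors taken with IMP; (2) concomitant drugs of interest for possible interaction with IMP; (3) "Concomitant medications that are commonly co-administered for the treatment of PAH".

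The protocol uses a different concept. Section 10.6: "Concomitant medications (medications present while on study drug) will be recorded throughout the study". Section 7.13: "Concomitant therapy includes any prescription and/or nonprescription medications taken in combination with study drug". Neither refers to a start date. Section 1 of the SAP says that the SAP supersedes the protocol's statistical considerations, so the SAP wording governs the tables.

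**The concern.** A concomitant-medication table is read as a record of what subjects took while on study drug. A definition that depends on starting after first dose answers a different question: which drugs were newly begun. The gap matters more here than in most trials because this is an add-on study. Background PAH therapy is in place before dosing by design and is meant to stay unchanged.

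At stake is how far the report can describe co-medication and potential drug interactions. A reader looking for subjects who took an interacting drug together with IMP would not find long-standing users in the concomitant table. In the prior table those users could not be told apart from subjects who had stopped the drug before dosing.

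**Working it through.** No arithmetic applies. The check is to apply each document's rule to the possible histories of a drug relative to IMP dosing.

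| History of the drug | SAP prior | SAP concomitant | Protocol concomitant |
|---|---|---|---|
| Stopped before first dose | yes | no | no |
| Started before first dose, continued on IMP | yes | **no** | **yes** |
| Started after first dose, while on IMP | no | yes | yes |
| Started after last dose, subject still in study | no | yes | no |

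1. Rows 1 and 2 receive identical SAP labels, although only the drug in row 2 was taken with IMP. This is the core defect.
2. Row 2 is where the SAP leaves out what the protocol includes. Row 4 is the reverse: the SAP includes therapy begun off drug, because its wording runs to the end of the study and SAP 6.4.2 lets subjects stay in the study off IMP. The SAP concomitant table is therefore not a record of overlap in either direction.
3. How common is row 2 for PAH drugs? Protocol 5.2 requires: "Subjects receiving additional FDA approved PAH therapies must be stable on their current dose for at least 30 days prior to the Baseline Visit". The same section requires 90 days of uninterrupted inhaled treprostinil before randomization. Protocol 6.6 bars adding PAH therapy during the study except for medical necessity. Together these rules place most background PAH therapy in row 2. Neither document gives counts of ERA, PDE-5 inhibitor, riociguat or transporter-inhibitor use, so no percentage can be attached.
4. Optional tabulations. Tables 2 and 3 use the defined term, so on a strict reading they miss drugs ongoing at first dose. Table 1 does not use the term and refers to use with IMP. That could include ongoing inhibitors but sits awkwardly beneath the definition, so it is ambiguous.
5. Are the data available? Protocol 7.2: "Current prescription and/or nonprescription medications will be assessed and entered in the concomitant medications CRF". Drugs current before dosing are therefore already collected, and SAP 6.4.1 already relies on this CRF to settle the treprostinil stratum. What is missing is a classification rule, together with a rule for partial medication dates; the imputation rule in SAP 7.2.2 covers adverse-event onset only.

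**The case against.** The strongest reply is that little is lost. Drugs ongoing at first dose still appear by treatment group in the prior table. SAP 6.7.2 describes ERA, PDE-5 inhibitor, riociguat and inhaled treprostinil background at randomization. Background PAH therapy is also a subgroup factor in 6.8 and 6.15, and 7.1 presents inhaled treprostinil use during the study. The three extra tabulations are optional. SAP 6.2 promises an addendum on data conventions before unblinding, which could settle how ongoing drugs are classed.

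Most of this stands, and it limits the point. A reader might infer that background PAH drugs vanish from the report; they do not. A reader might infer that every interaction table would show new starts only. That is not established, because table 1 is worded by use with IMP. A reader might also infer that the concomitant table would track clinical outcome, since PAH additions need medical necessity. That is plausible but speculative, and a list of added therapy beside the baseline table has its own use. A claim that nearly all background use is missed would be an inference from the entry rules, not a figure in the documents.

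The reply does not close the gap. The 6.7.2 table is a snapshot at randomization of PAH classes only. It does not show continuation on IMP, and it does not cover transporter inhibitors, other interacting drugs, anticoagulants or diuretics. The main concomitant table is not optional. The addendum is not among the documents, and its stated purpose is to implement the SAP, not to replace a definition the SAP has already given.

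**Conclusion.** The point holds as a minor defect of definition. SAP 6.7.4.2 contradicts protocol 10.6 and 7.13, and the two planned tables cannot show what was taken alongside IMP. Optional tables 2 and 3 share the problem on a strict reading; table 1 is ambiguous.

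The effect is confined to descriptive and drug-interaction summaries. No endpoint, analysis set or hypothesis test uses the definition. That most background PAH therapy falls outside it is a well-supported expectation. It assumes that subjects were enrolled and maintained according to the entry and stability rules.

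**What to change.** Amend SAP 6.7.4.1 and 6.7.4.2 before unblinding:

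- **Concomitant:** any medication taken on or after the first IMP dose during the study, whatever its start date, including those ongoing at first dose. Flag medication started after the last IMP dose separately. Simply ending the window at the last dose would drop therapy begun after IMP stops while the subject is still followed.
- **Prior:** any medication started before the first IMP dose, with an ongoing/stopped flag. Continuing drugs then appear in both tables.
- **Interaction and co-medication tabulations:** define by overlap with IMP dosing, from first to last dose.
- **Partial dates:** state a rule for incomplete medication start and stop dates.

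The cost is a few sentences across two SAP sections plus the matching programming. The addendum planned in SAP 6.2 could carry the partial-date rule; the definitions themselves belong in the SAP. No new data collection is needed.
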